## 6. Research Plan

**6.1 Study timetable and logistics.** The study will consist of an intake-training session and a 4-week intervention phase. Participants will complete brief weekly online surveys during the intervention phase and a follow-up online survey 4-weeks after the end of the intervention period. Face-to-face interaction with subjects will take place at the University of Florida McKnight Brain Institute (MBI) during the intake-training visit, the return of study equipment, and the distribution of participant payment

**Figure 1** Visualization of the study protocol and timeline.

**6.2 Experimental design.** As participants are scheduled for intake visits, they will be assigned to either a tVNS group (tVNS + mindfulness or sham + mindfulness) or a non-tVNS group (mindfulness only or control) by the research coordinator based on practical considerations (i.e. tVNS device availability) to expedite study completion. Within each of these groups, participants will be randomized via alternating order to either the active or control condition (in other words, once a participant is assigned to a tVNS group, they will then be randomized to either the tVNS + mindfulness or sham + mindfulness group). This process will repeat until each group has the target number of participants.

In the initial visit, a research assistant will review the appropriate informed consent form. During this process, participants assigned to a stimulation group (tVNS + mindfulness or sham + mindfulness) will be told that they have been randomized to receive one of two different types of noninvasive vagal nerve stimulation, that we think one of the conditions may be more effective, and that they have a 50/50 chance of being in that group. For participants randomized to the non-stimulation groups (mindfulness only or control), they will be told that they have been randomly assigned to use one of two mobile app interventions, that we think one of the interventions may be more effective, and that they have a 50/50 chance of being in that group. After providing written informed consent, participants will complete a brief health questionnaire as part of our inclusion/exclusion screening (see section 6.5). If participants screen out after signing the informed consent, the session will end, and any data collected will be kept in a locked filing cabinet.

After passing the screening, participants will complete an online survey that will include measures of mood, well-being, pain, daytime sleepiness, and sleep quality (see section 6.6 for specific measures).

These measures are self-report and will establish a baseline for each participant. They will be provided with and trained on the following equipment depending on their group assignment:

- **Brightmind Meditation mobile mindfulness app** (Brightmind Meditation, LLC; <https://www.brightmind.com>): Participants in each of the three active treatment groups (tVNS + mindfulness, sham + mindfulness, and mindfulness-only) will be provided with free access to the Brightmind mobile mindfulness app. During the intake session, they will download the app and complete an orientation to learn its features. They will be asked to practice mindfulness meditation through the app for 10 minutes each evening during the 4-week

intervention phase, with compliance defined as using the app 10 minutes/day for at least 4 days/week.

- **Control task:** Participants in the control group will be provided with the link and instructions for a control task (an online number puzzle: <https://play2048.co/>) that has been used in previous studies of mindfulness apps. They will be asked to engage with this control task for 10 minutes each evening during the 4-week intervention phase, with compliance defined as engaging with the task 10 minutes/day for at least 4 days/week. Participants in the control group will receive free access to the Brightmind mindfulness app after study completion.
- **Soterix Medical RELifit-Tragus Device** (Soterix Medical Inc.; <https://soterixmedical.com/research/tavns>): Participants in the tVNS + mindfulness and sham + mindfulness groups will be provided with the Soterix Medical RELifit-Tragus device, as well as its accompanying equipment (e.g., device charger, gel, cleaning materials). During the intake session, they will be trained on procedures for using the device, including gel application, electrode placement, and device configuration. Once the research assistant confirms that the participant understands how to apply the electrodes and set the stimulator, the research assistant will demonstrate how to take a picture of the electrode application to check the quality of the application. Participants will be instructed to take a picture that hides the identifying features of the face. Participants will be asked to administer tVNS concurrently with mindfulness practice for at least 4 days per week for the first 2 weeks of the intervention phase. They will be asked to send a picture of the application of the electrodes for each stimulation session. If a picture of the application indicates improper placement, a research assistant will contact the participant via phone or email to review proper form.
- **Fitbit Wristband** (Fitbit LLC): All participants will be provided with a Fitbit wristband for overnight sleep and HRV measurement. They will be instructed on the best method for wearing the band during the initial visit. Participants will be asked to wear the wristband overnight each night for the 4-week intervention phase, with compliance defined as wearing the device overnight at least 4 nights/week.
- **Polar H10 Chest Strap** (Polar Electro; [https://www.polar.com/us-en/products/accessories/h10\\_heart\\_rate\\_sensor](https://www.polar.com/us-en/products/accessories/h10_heart_rate_sensor)): All participants will be provided with a Polar H10 chest strap for HRV measurement during mindfulness practice. They will be instructed on the best method for wearing the chest strap during the initial visit. In addition, the research assistant will assist them in downloading a mobile app for data collection/storage and pairing it with the Polar H10 band for HRV recording. They will be asked to wear the chest strap during at least one mindfulness practice session per week during the 4-week intervention period.

After receiving study equipment and completing training procedures, participants will begin the intervention phase at home. They will be provided with written and/or video instructions as a reminder of procedures for the intervention phase depending on their group (summarized in **Table 1**). Study staff will also be available to answer questions or provide reminders via email and/or phone. During the intervention phase, participants will complete brief weekly online surveys consisting of some of the measures administered at baseline (see section 6.6). The survey will be sent via an electronic link to participants' email address or phone number. At the completion of the 4-week intervention phase, the research assistant will coordinate with the participant to schedule a time to return study equipment and distribute participant payment. Participants will be compensated for their time and effort (see section 10).

Group	Intervention Phase Procedures
-------	-------------------------------

tVNS + mindfulness (n = 20)	
 
- Practice mindfulness meditation through the Brightmind Meditation app for 10 minutes each evening for 4 weeks
 
- Administer tVNS concurrently with mindfulness practice at least 4 days per week during the first 2 weeks of the intervention phase
 
- Wear the Polar H10 chest strap during mindfulness practice at least 1x/week
 
- Wear the Fitbit overnight for 4 weeks
 

Sham + mindfulness (n = 20)	
 
- Practice mindfulness meditation through the Brightmind Meditation app for 10 minutes each evening for 4 weeks
 
- Administer sham stimulation concurrently with mindfulness practice at least 4 days per week during the first 2 weeks of the intervention phase
 
- Wear the Polar H10 chest strap during mindfulness practice at least 1x/week
 
- Wear the Fitbit overnight for 4 weeks
 

Mindfulness only (n = 20)	
 
- Practice mindfulness meditation through the Brightmind Meditation app for 10 minutes each evening for 4 weeks
 
- Wear the Polar H10 chest strap during mindfulness practice at least 1x/week
 
- Wear the Fitbit overnight for 4 weeks
 

Control (n = 20)	
 
- Engage with the control task for 10 minutes each evening for 4 weeks
 
- Wear the Polar H10 chest strap during the control task at least 1x/week
 
- Wear the Fitbit overnight for 4 weeks
 

**Table 1.** Intervention phase procedures for each experimental group.

**6.3 Subjects.** This study utilizes a between-participant design and will recruit 80 healthy college students aged 18 – 30. Pregnant women may not participate in this study—pregnancy tests provided by the study will be used for women of child-bearing age randomized to a tVNS group prior to starting the study and after the consenting process. Pregnancy tests will only be given in the intake session.

**6.4 Recruitment and Retention.** We will recruit a volunteer sample of undergraduate students from the Gainesville, Florida community who are interested in managing stress. We will post IRB-approved flyers around the community and on the UF campus. The flyers include a survey link where interested students can provide their contact information if they believe they qualify for the study to allow study staff to contact them to schedule an intake appointment. The investigators will be involved in recruitment of participants from multiple sources, including campus tabling events, posting flyers on UF campus and through GatorWell, emails to relevant listservs, making announcements during undergraduate classes, and through word of mouth. The investigators will also post announcements to Facebook and Twitter (see Social Media Strategy). Subjects will be expected to provide their own means of transportation.

**6.5 Inclusion/Exclusion Criteria.** Participants will include adults between the ages of 18-30, consistent with the typical college population. Participants must own a smartphone, be able to read and write English, and not be in ongoing psychotherapy.

Major medical illnesses including diagnosed severe neurological illnesses (e.g., stroke, seizure history), medical conditions associated with neurological effects (e.g. heart, kidney disease), autoimmune disorders, and severe psychiatric diseases (e.g., schizophrenia) will be excluded. Participants with any history of brain surgery, tumor, intracranial metal implantation, pacemakers or other implanted devices will be excluded. These elements will be assessed via self-report.

Sleep medications and/or psychotropic medications are exclusionary. Current illicit or prescription drug abuse (within the last two months) will result in exclusion or delay. Marijuana or alcohol abuse >2 weeks out will be acceptable for inclusion. Participants who are pregnant will be excluded. If participants have a history of adverse reaction to electrical nerve stimulation, they will be excluded.

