*Acceptability of Intervention Measure (AIM), Intervention Appropriateness Measure (IAM), and Feasibility of Intervention Measure (FIM).* These brief 4-item scales measures the degree to which participants believe an intervention is acceptable, appropriate, and feasible. These measures will only be given after the completion of the intervention phase (week 4).

**Physiological.** Subjects will be given a Fitbit brand wristband that offers real-time physiological data acquisition to use to monitor their sleep quantity, quality, and overnight heart rate variability (HRV) during the intervention phase. Participants will also be given a Polar H10 chest strap to use during mindfulness sessions, measuring their momentary HRV. Participants may be provided a preassigned account and password for these wearable devices, which may be accessed by the research team to manage raw data.

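### No between-arm comparison has a random step: device availability sets the tVNS or non-tVNS pair, and alternation, labelled randomised, sets the arm within it

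*Combined protocol and SAP*

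**What the plan says.** Section 6.2 (Experimental design) describes two steps.

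- **Pair.** "As participants are scheduled for intake visits, they will be assigned to either a tVNS group" or to a non-tVNS group. The choice is made "by the research coordinator based on practical considerations (i.e. tVNS device availability) to expedite study completion". It is made at scheduling, so it comes before consent, screening and the baseline survey.
- **Arm within the pair.** "Within each of these groups, participants will be randomized via alternating order to either the active or control condition".

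For the pair step the main sentence uses the word assigned. Two later phrases treat that step as randomised: "For participants randomized to the non-stimulation groups (mindfulness only or control") in the consent paragraph of Section 6.2, and, on pregnancy tests in Section 6.3, "will be used for women of child-bearing age randomized to a tVNS group". The consent paragraph also has participants told that they have already been randomised, with an even chance of either arm of their pair.

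Section 5 states the comparisons. The overall goal sets the combined intervention against mindfulness-only and control. Hypotheses 4.1 and 4.2 set it against sham and control. Hypotheses 2.1 and 2.2 set mindfulness-only against control. The Analysis Plan in Section 6.6 fits linear and quadratic time trends with group as moderator, and also compares acceptability, dropout, retention and adherence by group. It has no enrolment-period term and no caveat about how the groups were formed.

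Under Nerve Stimulation in Section 6.6, blinding is stated for participants only, and participants can be removed at calibration. The text describes no random sequence, no holder of the sequence and no concealment.

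**The concern.** A comparison between arms is protected against prior differences only if chance decided who went where. Here two different mechanisms stand in for chance.

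**Across pairs.** Device availability can vary over the calendar, and stress, mood and sleep in students may vary with the point in the academic term. If the pairs enrol at different times, a difference between tVNS + mindfulness and control mixes treatment with period. Removal at calibration adds to this, because only the tVNS pair is calibrated. The same split runs through the group comparisons of acceptability, dropout, retention and adherence.

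**Within pairs.** Alternation is a fixed rule. Staff who know the last assignment and who schedule, consent or screen can foresee the next arm, and could influence who receives it, even without intent. In the non-tVNS pair the arm is evident to the staff who train participants on the app or the puzzle.

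Aims 2 and 4 exist to produce effect sizes, and Section 5 says such data will inform future trials. A confounding shift enters an effect size one for one.

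**Working it through.** **Inputs.** From the documents: four arms of 20 (Table 1) and 80 in total (Section 6.3); 4 × 20 = 80, so these agree. The plan states no alpha, power, SD or target effect, so there is no figure of its own to reproduce. Assumptions made here: two-sided 0.05 and the shifts listed in step 4.

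**1. Which comparisons contain a random step?** Four arms give six pairwise comparisons.

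| Type | Comparisons | Basis |
|---|---|---|
| Within pair (2) | tVNS vs sham; mindfulness-only vs control | alternation |
| Across pairs (4) | tVNS vs mindfulness-only; tVNS vs control; sham vs mindfulness-only; sham vs control | device availability, then alternation |

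None of the six has a random step. Of the four cross-pair comparisons, Section 5 states tVNS vs control and tVNS vs mindfulness-only.

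**2. Predictability.** With alternation in two pairs, only the first allocation in each is not fixed by the one before: (80 − 2)/80 = 78/80 = 97.5%. If screen-outs use up places and 90 or 100 are allocated, it is 88/90 = 97.8% or 98/100 = 98.0%.

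For permuted blocks, 40 allocations per pair were simulated, always guessing the arm with fewer participants so far:

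| Block sizes, chosen at random | Correct guesses |
|---|---|
| 2, 4, 6 | 70% |
| 4, 6 | 69% |
| 4, 6, 8 | 68% |

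These figures assume that past assignments are visible under both schemes. If they are not visible, both are near 50%. They measure predictability, not bias.

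**3. Precision at 20 versus 20.** The 95% half-width for a standardised difference near zero is 1.96 × √(2/20) = 0.62 SD, or 2.024 × √(2/20) = 0.64 SD with t on 38 degrees of freedom.

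**4. Illustrative effect of a confounding shift.** Suppose there is no treatment effect, but the pairs differ in change by δ SD. The t statistic on 38 degrees of freedom then has noncentrality δ/√(2/20).

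| δ (assumed) | Noncentrality | False rejection | 95% coverage |
|---|---|---|---|
| 0.2 | 0.63 | 9.5% | 90.5% |
| 0.3 | 0.95 | 15.2% | 84.8% |
| 0.5 | 1.58 | 33.8% | 66.2% |

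Each of these shifts is smaller than the half-width in step 3, so the data could not separate it from an effect.

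**5. What the planned models remove.** Over four equally spaced values, the linear contrast has weights −3, −1, 1, 3 and the quadratic 1, −1, −1, 1. Both sum to zero, so a constant difference in level between pairs drops out of the group-by-time terms. This holds for surveys, where "These measures are self-report and will establish a baseline for each participant", and equally for repeated Fitbit values. A simulated check with four weekly values and a constant prior difference of 0.5 SD left rejection at about 5% for both contrasts. A difference between pairs in change does not drop out, and step 4 describes that case.

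**The case against.** **It is a pilot that seeks effect sizes and discloses its mechanism.** That is fair on tone, and the governing sentence does say assigned for the pair step. But modest aims do not make alternation random, and biased effect sizes would pass into the trials they are meant to inform.

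**Nothing links device availability to prognosis.** This stands. Equipment is returned after each 4-week phase, so the pairs may well interleave. The number of devices is not given. The shifts above are assumptions, and no bias has been shown.

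**Stronger readings that a reader might infer, and that the documents do not support:**

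- *The sequence is open to staff.* The text describes no concealment, but it does not say that the list is visible. What can be said is that alternation is predictable to anyone who knows the last assignment.
- *The protocol consistently calls both steps randomised.* It does so for the arm step. For the pair step the label comes only from the two later phrases.
- *Fitbit comparisons across pairs are badly inflated because there is no baseline.* It is true that "Participants will be asked to wear the wristband overnight each night for the 4-week intervention phase", and that the device is there to "monitor their sleep quantity, quality, and overnight heart rate variability (HRV) during the intervention phase", so there is no pre-intervention value. But Hypothesis 4.1 concerns improvement and the plan models time trends, from which a constant level difference cancels. Only a comparison of Fitbit levels would carry that difference, and the plan states none across pairs. The level wording for overnight HRV in Hypothesis 2.2 is within a pair.
- *Pregnancy testing makes the pairs materially different.* Pregnancy excludes everyone under Section 6.5; only the study test is confined to the tVNS pair.
- *Calibration removals bias tVNS vs sham.* The ramp is common to both arms, so they need not.

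**Conclusion.** The plan is wrong as written. Within-pair allocation is systematic but labelled randomised, and pair allocation is a practical choice that two phrases label randomised. This follows from the text alone and needs no assumption.

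The consequences differ in kind. Within a pair the exposure is predictability: 97.5% against 68% to 70%, if past assignments are visible. Across pairs it is confounding by enrolment period and by tVNS-only removals. Its size is unknown, because the documents give neither enrolment dates nor a removal rate. The false rejection rates of about 9.5% to 34% rest on assumed shifts of 0.2 to 0.5 SD in change, 20 per arm and a two-sided 0.05 level. They show what such shifts would do, not what will happen.

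Replacing alternation and correcting the label are necessary before any between-arm result is reported as randomised, since analysis cannot supply a missing random step afterwards.

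**What to change.** **(a) Arm within pair.** Replace alternation with a computer-generated permuted-block list for each pair, with random, undisclosed block sizes. Conceal it from staff who schedule, consent and screen, for example by holding it in the study database. Reveal the arm only after consent, screening and the baseline survey and, in the device pair, after the pregnancy test and the common calibration ramp. Change the consent wording so that participants are told they will be randomised between the two arms of their pair, not that they already have been.

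**(b) Pair.** If the coordinator continues to assign it, remove the word randomised for that step in Sections 6.2 and 6.3. Once (a) is in place, limit randomised claims to tVNS vs sham and mindfulness-only vs control. Report all cross-pair comparisons as non-randomised, including those of acceptability, dropout, retention and adherence, and show enrolment dates and post-assignment removals by pair.

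**Optional.** Adjust cross-pair comparisons for enrolment period as a sensitivity analysis. With two periods (assumed) and shares p and 1 − p of the two arms enrolled in the first, the standard error is multiplied by 1/√(1 − φ²), where φ = 2p − 1:

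- 60% vs 40%: φ = 0.2, factor 1.02
- 75% vs 25%: φ = 0.5, factor 1.15
- 90% vs 10%: φ = 0.8, factor 1.67

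Without overlap no adjustment is possible, and the comparison should be descriptive. At 20 per arm this is a trade-off, not a requirement.

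**Cost.** Setting up the list, a short amendment with a consent wording change, and more modest cross-pair claims. Device-driven scheduling can stay.

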The current study explores using tVNS as a potential method to alleviate barriers to establishing a habit of mindfulness practice. In mindfulness interventions it is not uncommon for participants to report an initial escalation of anxiety and distress as they directly engage with negative thoughts. While accepting, decentering, and deriving meaning from these negative reactions is an important feature of the psychotherapeutic process in mindfulness interventions, they can also lead to disengagement or drop out from the intervention. Similarly, difficulty learning the skill of meditation is also common and can contribute to participant dropout. tVNS may exert an anxiolytic effect through effects on limbic structures and activation of the parasympathetic nervous system. Moreover, tVNS increases positive affect (i.e. calm) and has been linked to improved interoceptive awareness, which are two other potential psychological mediators of mindfulness interventions. Thus, these two separate treatment approaches appear complementary, yet there are no published trials using them in combination. **The proposed study will enable us to evaluate the utility of this combined treatment approach in enhancing college student sleep and mental health, with potentially broader impacts for clinical populations.**

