Though digital mindfulness interventions offer many potential sleep and mental health benefits for college students, rates of adherence and sustained use of mindfulness apps have been low. Thus, more research needs to examine facilitators to the uptake and sustainability of mindfulness practice, as well as complementary treatment methods that can boost the perceived effectiveness of mindfulness practice. The current study explores tVNS as one such complementary treatment. tVNS is a safe, non-invasive form of vagus nerve stimulation (FDA-approved for the treatment resistant depression and epilepsy). tVNS targets the auricular branch of the vagus nerve through stimulation at sites of the external ear, such as the inner tragus. It has been shown to affect vagally mediated components of the limbic system that are critical to sleep and mood via activation of the nucleus of the solitary tract (NTS). Moreover, tVNS has been shown to increase parasympathetic tone, which can have a beneficial effect on both sleep and mood. Stimulation of the vagus nerve has been associated with reductions in daytime sleepiness, decreased sleep latency, greater slow wave sleep, and longitudinal improvements in self-reported sleep quality in clinical and preclinical studies. tVNS has also been associated with improvements in anxiety and depressive symptoms. Thus, tVNS may be a convenient means to improve sleep and mental health outcomes among college students engaging in mindfulness practice, although this potential has not yet been empirically tested. The current study will evaluate the feasibility, acceptability, and efficacy of this novel combined treatment approach relative to mindfulness-only and control conditions.

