## 5. Specific Aims

The goal of the proposed research project is to explore the acceptability and efficacy of a combined transcutaneous vagus nerve simulation (tVNS) and mindfulness intervention in enhancing sleep and well-being among college students and compare it to mindfulness-only and control conditions with the hypothesis that the combined intervention will have greater efficacy due to synergistic brain effects of tVNS and mindfulness. In addition to experimental results, the proposed project will

generate effect size data to inform future trials of the combined approach and assess the feasibility and acceptability of our study design.

**Specific Aim 1:** To evaluate the feasibility and acceptability of sustained engagement with the Brightmind mindfulness app among college students.

Research question 1.1: Do students find this app acceptable and engage with it consistently across a 4-week period?

Research question 1.2: What are the barriers and facilitators to sustained engagement with the app?

Hypothesis 1.3: Participants who spend more time engaging with the app will see greater improvements in mental health (e.g., stress, anxiety, depressive symptoms, positive affect) and HRV compared to participants who spend less time engaging with the app.

**Specific Aim 2:** To obtain preliminary effect size data on the efficacy of the Brightmind mindfulness app in improving proximal and distal mental health outcomes among college students

Hypothesis 2.1: Participants in the mindfulness-only group will demonstrate greater improvements in mental health (e.g., stress, anxiety, depressive symptoms, positive affect) than participants in the control group

Hypothesis 2.2: Overnight heart rate variability (HRV), positive affect, and interoceptive awareness will be greater in the mindfulness-only group compared to the control group.

Hypothesis 2.3: HRV will increase from before to after each mindfulness session.

**Specific Aim 3:** Determine feasibility and acceptability of the combined tVNS + mindfulness intervention.

Research question 3.1: Do students find this combined intervention acceptable and demonstrate adequate adherence (i.e. use tVNS or sham + mindfulness for at least 10 minutes/day at least 4 days/week for 2 weeks)?

Research question 3.2: What are the barriers and facilitators to adherence with the combined intervention?

Hypothesis 3.3: The combined intervention will be well-tolerated and receive positive acceptability ratings.

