**7.3 Mood Assessments:** Questions about mood and personality can sometimes be uncomfortable (e.g., talking about things that make you sad or anxious). If participants experience distress while completing these questionnaires, they will be instructed to contact a research assistant who will be able to provide community mental health resources.

**7.4 Wearable Sensors:** The wrist monitor is comparable to wearing a standard wristwatch. If the band is too tight, there is a risk of skin irritation. Similar risks apply to the chest band. Both bands are adjustable to ensure participant comfort.

**7.5 Breach of Confidentiality.** Breach of confidentiality is highly unlikely because all information will be identified with a participant code and stored in a locked file cabinet. Only study staff will have access to this database. All staff are or will be fully trained in relevant ethical principles and procedures, including confidentiality.

Once a participant completes the entirety of the study (i.e. returns the equipment and/or receives payment) and the payment is updated according to UF's Human Participant Payments guidelines, the subject's contact information and student identification/social-security-number will be redacted from the questionnaires and payment receipts.

**7.6 Data and Safety Monitoring Plan.** The investigative team will meet regularly to discuss data and safety monitoring issues. Any issues identified during the course of these meetings will be handled in a manner consistent with the University of Florida's policies.

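### The time at which controls receive the Brightmind app is not tied to the follow-up survey, so the text permits, but does not show, release before follow-up

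*Combined protocol and SAP*

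**What the plan says.** The control task paragraph in section 6.2 promises the active app to controls: "Participants in the control group will receive free access to the Brightmind mindfulness app after study completion". It names no week or visit and does not mention the follow-up survey.

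Three other places bear on when a participant has completed the study:

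- Section 7.5 (confidentiality) opens its redaction rule with "Once a participant completes the entirety of the study (i.e. returns the equipment and/or receives payment". This is the only place that spells out what completion means, and the follow-up survey is not part of it.
- Section 6.2 places equipment return, together with payment, after the intervention: "At the completion of the 4-week intervention phase, the research assistant will coordinate with the participant to schedule a time to return study equipment".
- Section 6.1 first describes the study as the intake session plus the 4-week intervention. Its next sentence adds weekly surveys and "a follow-up online survey 4-weeks after the end of the intervention period".

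Section 6.6 lists follow-up among the possible administration times of most self-report scales. The Analysis Plan fits linear and quadratic time trends with group as moderator. It does not say whether the follow-up point enters these models.

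**The concern.** The control arm has 20 participants (Table 1), and every contrast with control rests on them. They are meant to be free of the app at each time point where they serve as the comparator. If they receive the app when they return equipment, the follow-up survey compares people who were given the app at intake with people who were given it about four weeks before the survey.

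The comparisons at stake are self-report contrasts with control that use follow-up data: Hypothesis 2.1, the self-report parts of Hypothesis 2.2 ("Overnight heart rate variability (HRV), positive affect, and interoceptive awareness will be greater in the mindfulness-only group compared to the control group"), and the self-report control comparisons in Hypotheses 4.1 and 4.2. Aims 2 and 4 exist to produce effect sizes for later trials, so a follow-up effect size with an unclear comparator would be carried forward. Once a control has used the app, that person's unexposed follow-up score cannot be recovered.

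**Working it through.** The plan states no figure to reproduce on this point. The check is a timeline, a list of the outcomes touched, and a look at how far a follow-up value would spread through the planned model.

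**1. Timeline, literal reading**

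- End of intervention: week 4 (section 6.1).
- Completion as defined in section 7.5: equipment return and/or payment, arranged once the intervention ends (section 6.2), so about week 4. The exact day is not fixed.
- Follow-up survey: 4 + 4 = week 8 (section 6.1).
- Longest time with the app before follow-up: 8 − 4 = 4 weeks, or 4 × 7 = 28 days. It shortens by any delay in return or payment.

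**2. Passages side by side**

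For the week-4 reading:

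- the definition in section 7.5;
- the first sentence of section 6.1, which describes the study as intake plus a 4-week phase.

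Against it:

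- At the start of section 6.2 the same two-word phrase for completion is used of the whole trial, as the aim that assignment by device availability is meant to speed up.
- In section 6.6 the PSQI and ESS are said to track change over the study period, and their listed times include follow-up.
- Where the protocol means week 4 it has separate wording, in section 6.2 (equipment return) and in section 6.6 (the SUS and the AIM, IAM and FIM), and refers to the intervention phase.

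No passage says that the app is withheld until follow-up, and none says that it is handed over at equipment return.

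**3. Outcomes touched**

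Scales that match a control hypothesis and list follow-up in section 6.6:

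- PSS, GAD-7 and PHQ-8 (Hypotheses 2.1 and 4.2);
- PANAS (Hypotheses 2.1, 2.2 and 4.2);
- MAIA-2 (Hypothesis 2.2);
- PSQI (Hypothesis 4.1).

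That makes six. The Fitbit is worn only during the 4-week intervention phase, so its sleep and overnight HRV data end before any release. The tVNS versus sham contrast does not involve controls.

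**4. Spread through a quadratic trend**

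This applies only if follow-up enters the model. As an illustration, take an ordinary equal-weight least-squares quadratic in time, not the full multilevel model, with H = X(X′X)⁻¹X′ and columns 1, t, t².

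- Visits at weeks 0, 2, 4 and 8: the residual direction is (−3, 8, −6, 1), with squared length 9 + 64 + 36 + 1 = 110. The leverage of week 8 on itself is 1 − 1/110 = 0.99. Its weight in the fitted week-4 value is 6/110 = 0.055.
- Visits at weeks 0, 1, 2, 3, 4 and 8: the corresponding values are 0.99 and 0.072.

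A shift in the control mean at week 8 would therefore pass almost whole into the fitted week-8 contrast. About 5 to 7% of it would reach the fitted week-4 value. Observed week-4 data would not change. This shows where an effect would land, not how large it would be.

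**The case against.** The strongest reply is that release after follow-up is at least as natural a reading. The confidentiality paragraph was written to time the redaction of identifiers, and the control task paragraph does not cite it. The same phrase in section 6.2 means completion of the trial, the PSQI and ESS descriptions count follow-up within the study, and the protocol had other words available for week 4. Figure 1 and the consent form were not available for this check, and either may settle the timing. Payment details are also left to other records (section 10).

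Most of this stands. It rules out a stronger statement that a reader might infer, namely that the plan gives controls the app at week 4. The documents do not show that. The reply does not remove the ambiguity, because the only explicit definition and the opening of section 6.1 both support the earlier date.

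A reader might also infer that the follow-up contrast would shrink by a calculable amount. The documents do not support that either. Controls are offered access and are not asked to practise; section 4 notes that "rates of adherence and sustained use of mindfulness apps have been low"; and no uptake or benefit is stated. Even the direction is open, since the Abstract says that in mindfulness interventions "it is not uncommon for participants to report an initial escalation of anxiety and distress". The practice requested of the app arms says nothing about what controls would do.

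**Conclusion.** The concern holds as a conflict in the text about when controls receive the active treatment. The app could reach them up to about four weeks before the follow-up survey, but early release is not shown to be planned.

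The consequence depends on several conditions: early release, actual use, an effect of that use on the scales, and use of the follow-up point in the analysis. If all of them held, self-report comparisons with control at follow-up, and trends fitted through it, would no longer compare app with no app. The size and direction cannot be taken from the documents.

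If Figure 1 or the consent form already places release after follow-up, the only change needed is for section 6.2 to say the same.

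**What to change.** In the control task paragraph of section 6.2, state that controls receive the app only after their follow-up survey is received or its window closes.

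If any control receives it earlier, record the date of access and add a sensitivity analysis that leaves out that control's follow-up data. The main follow-up comparison need not be abandoned because of one early release.

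The cost is one clause in section 6.2, a date field for app access, and a wait of up to about four more weeks for controls.
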